## **6.5 Dose escalation and dose modification**

Investigational or other study treatment dose adjustments and/or interruptions are not permitted. Please refer to [Section 6.1](#) for treatment guidance.

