Study treatment	Any drug or combination of drugs or intervention administered to the study participants as part of the required study procedures; includes investigational drug(s), control(s) or background therapy
Study treatment discontinuation	When the participant permanently stops taking any of the study drug(s) prior to the defined study treatment completion date (if any) for any reason; may or may not also be the point/time of study discontinuation
Treatment arm/group	A treatment arm/group defines the dose and regimen or the combination and may consist of 1 or more cohorts.
Treatment of interest	The treatment of interest and, as appropriate, the alternative treatment to which comparison will be made. These might be individual interventions, combinations of interventions administered concurrently, e.g. as add-on to standard of care, or might consist of an overall regimen involving a complex sequence of interventions. This is the treatment of interest used in describing the related clinical question of interest, which might or might not be the same as the study treatment.
Variable (or endpoint)	The variable (or endpoint) to be obtained for each participant that is required to address the clinical question. The specification of the variable might include whether the participant experiences an intercurrent event.
Withdrawal of study consent (WoC)	Withdrawal of consent from the study occurs only when a participant does not want to participate in the study any longer and does not allow any further collection of personal data

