#### **9.1.1 Study treatment discontinuation and study discontinuation**

Discontinuation of study treatment for a participant occurs when study treatment is stopped earlier than the protocol planned duration and can be initiated by either the participant or the investigator.

The investigator must discontinue study treatment for a given participant if, he/she believes that continuation would negatively impact the participant's well-being.

Study treatment must be discontinued under the following circumstances

- Participant/guardian decision
- Use of prohibited treatment as per recommendations in the prohibited treatment section
- Any situation in which study participation might result in a safety risk to the participant
- Following emergency unblinding

- Emergence of adverse events that in the judgment of the investigator, taking into account the participant's overall status, prevent the participant from continuing participation in the study
- Any laboratory abnormalities that in the judgment of the investigator, taking into consideration the participant's overall status, prevents the participant from continuing participation in the study
- Severe hypersensitivity reaction occurs, including any of the following: anaphylaxis, fever, chills, urticaria, dyspnea, headache, myalgia, hypotension. Immediate interruption of the infusion to administer study treatment is required in such cases.

If discontinuation of study treatment occurs, the investigator should make a reasonable effort to understand the primary reason for the participant's premature discontinuation of study treatment and record this information.

Participants who discontinue study treatment or who decide they do not wish to participate in the study further should NOT be considered withdrawn from the study UNLESS they withdraw their consent (see 'Withdrawal of Informed Consent' section). **Where possible, they should return for the assessments indicated** in the Assessment Schedule. If they fail to return for these assessments for unknown reasons, every effort (e.g. telephone, e-mail, letter) should be made to contact the participant/pre-designated contact as specified in the lost to follow-up section. This contact should preferably be done according to the study visit schedule.

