## 10.2 Additional Safety Monitoring

### 10.2.1 Liver safety monitoring

To ensure participant safety and enhance reliability in determining the hepatotoxic potential of an investigational drug, a standardized process for identification, monitoring and evaluation of liver events has to be followed.

Please refer to [Table 16-1](#) in [Appendix 3](#) for complete definitions of liver laboratory triggers.

[figure not shown]
Once a participant is exposed to study treatment, every liver event defined in [Table 16-1](#) should be followed up by the investigator or designated personnel at the trial site, as summarized below. Additional details on actions required in case of liver events are outlined in [Table 16-2](#). Repeat liver chemistry tests (i.e. ALT, AST, TBL, PT/INR, ALP and GGT) to confirm elevation.

- These liver chemistry repeats should be performed using the local laboratory used by the site. Repeated laboratory test results must be reported as appropriate.
- If the initial elevation is confirmed, close observation of the participant will be initiated, including consideration of treatment interruption if deemed appropriate.
- Hospitalization of the participant if appropriate
- Causality assessment of the liver event
- Thorough follow-up of the liver event should include
  - Based on investigator’s discretion: serology tests, imaging and pathology assessments, hepatologist’s consultancy; obtaining more detailed history of symptoms and prior or concurrent diseases, history of concomitant drug use, exclusion of underlying liver disease

All follow-up information and procedures performed must be recorded as appropriate in the CRF.

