### **2.1.1.3      End of study/end of treatment**

The end of study (EoS) date is the date when a patient completes or discontinues the study, i.e., the “Disposition Event Date” from the “disposition” CRF form for study disposition.

This is a one-time treatment study and disposition status based on the study treatment is not applicable.

For reporting data by visit in outputs, the discontinuation from study visit will be allocated to the visit number based on the day of EoS if discontinuation is on or before Day 29. For the

assessments that are scheduled on every other day and EoS visit falls on a day without scheduled assessment, the EoS visit will be mapped to next scheduled visit for the corresponding assessment. If the discontinuation from study is after Day 29, the EoS visit will be mapped to the next scheduled visit.

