### **2.4 Treatments (study treatment, rescue medication, concomitant therapies, compliance)**

#### **2.4.1 Study treatment / compliance**

There is only a one-time treatment given on Day 1 of the study. The number and percent of patients discontinued from study treatment, i.e., with an interruption due to adverse event during the 2-hour infusion and never restart the study treatment, will be summarized by treatment arm. The duration from Day 1 to the end of safety follow up will also be summarized based on the Day 29 data cut.

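### Protocol 6.5 bans infusion interruptions that 9.1.1 makes mandatory, and SAP 2.4.1 counts only adverse-event stops although the protocol defines treatment discontinuation as a stop for any reason

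*Protocol*

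**What the plan says.** **Stopping the infusion.** Protocol 6.5, the dose-modification section, reads: "Investigational or other study treatment dose adjustments and/or interruptions are not permitted". It then refers the reader to section 6.1, whose visible text gives the weight-based dose table and infusion time but no stopping or restarting guidance. Protocol 9.1.1 opens a list with "Study treatment must be discontinued under the following circumstances". The last item is severe hypersensitivity, followed by: "Immediate interruption of the infusion to administer study treatment is required in such cases". Section 10.2.1, on confirmed liver test elevations, calls for close observation, "including consideration of treatment interruption if deemed appropriate". Section 10.1.1 includes changing the dose and interrupting or withdrawing the drug among the possible responses to an adverse event.

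**What counts as discontinuation.** Protocol 9.1.1: "Discontinuation of study treatment for a participant occurs when study treatment is stopped earlier than the protocol planned duration", initiated by either the participant or the investigator. The protocol glossary: "When the participant permanently stops taking any of the study drug(s) prior to the defined study treatment completion date (if any) for any reason". SAP 2.4.1 narrows this. It describes discontinued patients as those "with an interruption due to adverse event during the 2-hour infusion and never restart the study treatment". SAP 2.1.1.3 says that, this being a one-time treatment study, "disposition status based on the study treatment is not applicable".

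**The concern.** There are two separate problems.

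First, the protocol contradicts itself on a safety action. One section forbids interruption outright and another makes it mandatory. Neither refers to the other or says which takes precedence. Staff at an infusion should not have to work that out. Whether a stopped infusion may be restarted is also open: 9.1.1 frames hypersensitivity as discontinuation, while the SAP's wording presupposes that restarts occur.

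Second, the SAP uses the protocol's term, treatment discontinuation, with a narrower meaning. A reader of the study report would take the tabulated figure to be the protocol-defined event, but part of that event is left out. At stake is an accurate account of how many infusions were permanently stopped, and why, for a single intravenous dose that protocol 4.2 itself calls relatively high.

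**Working it through.** The plan states no figure to reproduce. The check is a comparison of texts.

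**Step 1: do 6.5 and 9.1.1 govern the same act?** Section 6.1.1 puts total treatment duration at about two hours, and SAP 2.1.1 calls this a one-time treatment study. The ban on dose adjustments in 6.5 could refer to departing from the weight tiers in Table 6-1. The ban on interruptions can refer only to the infusion. Section 9.1.1 requires interruption of that infusion for severe hypersensitivity. Read literally, stopping breaches 6.5 and not stopping breaches 9.1.1.

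**Step 2: do other sections settle it?** No. Section 6.1 is silent in its visible text, and 6.6.2 says there is too little information for specific adverse-event treatment recommendations. Sections 10.1.1 and 10.2.1 mention interruption as a possibility, which does not fit 6.5 either. The liver text carries less weight: it asks only for consideration, and the infusion will usually have ended before a repeat liver test is available.

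**Step 3: which stops does each document count?**

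| What happens to the infusion | Protocol definition (9.1.1, glossary) | SAP 2.4.1 |
|---|---|---|
| Stopped for an adverse event, never restarted | Discontinued | Counted |
| Stopped for another reason, never restarted | Discontinued | Not counted |
| Interrupted, restarted and completed | Not discontinued (not a permanent stop) | Not counted |
| Completed without interruption | Not discontinued | Not counted |

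The documents disagree in the second row only. Section 9.1.1 lists seven circumstances that require discontinuation. At least three are not adverse events in themselves: participant or guardian decision, use of prohibited treatment, and emergency unblinding. During a two-hour infusion, the first is the most plausible.

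**Step 4: does another visible output pick up the second row?** SAP 2.8.1 tabulates adverse events that required stopping study treatment, which has the same limit. SAP 2.3.1 tabulates patients who received treatment and reasons for leaving the study. Leaving the study is a different event, because 9.1.1 says stopping treatment is not study withdrawal unless consent is withdrawn. SAP 2.1.1.3 declares treatment disposition not applicable, which conflicts with 2.4.1 summarising it. No visible output covers the second row.

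**Step 5: does it reach the efficacy analyses?** No. SAP 2.2 bases efficacy on the Full Analysis Set, as randomised, so an incomplete infusion removes nobody. The planned 450 patients, the power tables and the 0.05 level are untouched.

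**Step 6: scale.** The documents give no interruption rate. If 1% to 5% of infusions were interrupted or incomplete (an assumption, not an estimate), that would be 0.01 × 450 = 4.5 to 0.05 × 450 = 22.5 patients. The omitted group is only the permanent, non-adverse-event part of these, and its share is unknown.

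**The case against.** The best defence of the protocol is that it already protects patients. Section 9.1.1 obliges the investigator to stop treatment believed harmful to the participant, and 14.1 expects immediate safety action even where it departs from the protocol. A specific safety rule is naturally read as overriding a general line on dose modification. This stands against one tempting inference, that a site following 6.5 would continue an infusion through a severe reaction. The documents do not support that. The text conflict remains: the protocol never states the precedence, and 14.1 allows for acting despite a rule without removing the rule.

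The defence of the SAP also has force. Its section 2.4.1 is a counting definition and instructs no site. Excluding restarted infusions agrees with the glossary's requirement of a permanent stop, so a reader who inferred that restarted infusions are miscounted would be wrong. Nor does the SAP label partly dosed patients as fully treated, because it has no such category. Tolerability is not shown to be flattered: SAP 2.8.1 summarises treatment-emergent adverse events whether or not the infusion restarted. Protocol 6.6.1 on treatment compliance is redacted, the Pharmacy Manual is a separate document, and some outputs are specified only in the table shells. It therefore cannot be said that dose completeness goes uncollected. None of this supplies the missing non-adverse-event stops.

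**Conclusion.** Both parts hold in limited form. Protocol 6.5 and 9.1.1 contradict each other on stopping the infusion, 10.1.1 and 10.2.1 add to the inconsistency, and the visible protocol does not address restarting. SAP 2.4.1 undercounts treatment discontinuation against the protocol's own definition by leaving out permanent stops not caused by an adverse event, and SAP 2.1.1.3 does not agree with it.

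The consequence is confined to the consistency of the safety instructions and one descriptive exposure and compliance summary. The number of affected patients cannot be derived from the documents. The conclusion rests on the visible text: the redacted section 6.6.1 or the table shells might contain a fuller summary, but that would not resolve the protocol contradiction or the narrow wording of SAP 2.4.1. This review takes no position on which stopping or restarting rule is clinically right.

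**What to change.** 1. **Protocol.** Reconcile 6.5, 9.1.1, 10.1.1 and 10.2.1 so that all state or refer to one rule on interrupting, stopping and restarting the infusion. The clinical team decides the rule, including whether a restart is possible at all.
2. **SAP 2.4.1.** Define treatment discontinuation as in the protocol. Report the number and percentage of patients whose infusion was permanently stopped, by reason and by arm. Show interrupted-and-restarted infusions on a separate line where they were recorded.
3. **SAP 2.1.1.3.** Remove or qualify the statement on treatment disposition so that it agrees with 2.4.1.

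The cost is a short wording change in the protocol and one revised descriptive table. The reasons should largely be available, because 9.1.1 already asks investigators to record why treatment was stopped and to register the discontinuation in the IRT. Sample size, models and testing order stay as they are. The downside is that the reported discontinuation figure may rise slightly.

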## **6.6 Additional treatment guidance**

### **6.6.1 Treatment compliance**

[REDACTED]

### **6.6.2 Recommended treatment of adverse events**

At present there is insufficient information to provide specific recommendations regarding treatment of AEs in this patient population.

Medication used to treat adverse events AEs must be recorded on the appropriate CRF.

### **6.6.3 Emergency breaking of assigned treatment code**

Emergency code breaks must only be undertaken when it is required to in order to treat the participant safely. Blinding codes may also be broken after a participant discontinues treatment due to disease progression if deemed essential to allow the investigator to select the participant's next treatment regimen, and after discussion and agreement with the sponsor. Most often, study treatment discontinuation and knowledge of the possible treatment assignments are sufficient to treat a study participant who presents with an emergency condition. Emergency treatment code breaks are performed using the IRT. When the investigator contacts the system to break a treatment code for a participant, he/she must provide the requested participant identifying

[REDACTED]

information and confirm the necessity to break the treatment code for the participant. The investigator will then receive details of the investigational drug treatment for the specified participant and a fax or email confirming this information. The system will automatically inform the Novartis monitor for the site and the study team that the code has been broken.

It is the investigator's responsibility to ensure that there is a dependable procedure in place to allow access to the IRT/code break cards at any time in case of emergency. The investigator will provide:

- protocol number
- participant number

In addition, oral and written information to the participant must be provided on how to contact his/her backup in cases of emergency, or when he/she is unavailable, to ensure that un-blinding can be performed at any time.

## **6.7 Preparation and dispensation**

Each study site will be supplied with study drug in packaging as described under investigational and control drugs section.

Study drug will be packed and labeled as ACZ885 and supplied as open label bulk supplies. Each box will contain multiple vials of ACZ885 150mg/1ml. The box can be used for treatment of multiple patients. However, each vial intended for one patient should not be used for another patient.

Preparation of the investigational drug must be done in a separate space/room where study personnel have no access during time of preparation.

### **6.7.1 Handling of study treatment**

Study treatment must be received by a designated person at the study site, handled and stored safely and properly and kept in a secured location to which only the designated site personnel have access. Upon receipt, all study treatment must be stored according to the instructions specified in the IB.

Clinical supplies are to be dispensed only in accordance with the protocol. Technical complaints are to be reported to the respective Novartis Quality Assurance.

Medication labels will be in the local language and comply with the legal requirements of each country. They will include storage conditions for the study treatment but no information about the participant except for the medication number.

The pharmacist or other qualified site personnel must maintain an accurate record of the shipment and dispensing of study treatment in a drug accountability log which will be kept in a Pharmacy File in a secured location to which no blinded site staff would have access to.

Study treatment will be prepared by an independent pharmacist or qualified site personnel in order to ensure treatment blinding as described in [Section 6.1](#).

At the conclusion of the study, and as appropriate during the course of the study, the investigator will return all unused study treatment, packaging, drug labels, and a copy of the completed drug

accountability log to the Novartis monitor or to the Novartis address provided in the investigator folder at each site.

### 6.7.2 Instruction for prescribing and taking study treatment

Please refer to [Section 6.1](#) for treatment guidance.

## 7 Informed consent procedures

Eligible participants may only be included in the study after providing (witnessed, where required by law or regulation), Institutional Review Board (IRB)/ Independent Ethics Committee (IEC)-approved informed consent.

If applicable, in cases where the participant's representative(s) gives consent (if allowed according to local requirements), the participant must be informed about the study to the extent possible given his/her understanding. If the participant is capable of doing so, he/she must indicate agreement by personally signing and dating the written informed consent document.

Informed consent must be obtained before conducting any study-specific procedures (e.g. all of the procedures described in the protocol). The process of obtaining informed consent must be documented in the participant source documents.

Novartis will provide to investigators in a separate document a proposed informed consent form that complies with the ICH GCP guidelines and regulatory requirements and is considered appropriate for this study. Any changes to the proposed consent form suggested by the investigator must be agreed by Novartis before submission to the IRB/IEC.

Information about common side effects already known about the investigational drug can be found in the IB. This information will be included in the participant informed consent and should be discussed with the participant during the study as needed. Any new information regarding the safety profile of the investigational drug that is identified between IB updates will be communicated as appropriate, for example, via an Investigator Notification (IN) or an aggregate safety finding. New information might require an update to the informed consent and then must be discussed with the participant.

The following informed consents are included in this study:

- Main study consent (For US patients 12 - <18 years old; parental consent and adolescent assent)
- As applicable, Pregnancy Outcomes Reporting Consent for female subjects

Women of child-bearing potential must be informed that taking the study treatment may involve unknown risks to the fetus if pregnancy were to occur during the study.

It is required as part of this protocol that the Investigator presents this option to the participants, as permitted by local governing regulations. The process for obtaining consent should be exactly the same as described above for the main informed consent.

A copy of the approved version of all consent forms must be provided to Novartis after IRB/IEC approval.

## **8 Visit schedule and assessments**

The Assessment Schedule ([Table 8-1](#)) lists all of the assessments when they are performed. All data obtained from these assessments must be supported in the participant's source documentation.

Participants should be seen or phoned for all visits/assessments as outlined in the assessment schedule ([Table 8-1](#)) or as close to the designated day/time as possible. Missed or rescheduled visits should not lead to automatic discontinuation. At the day of discharge from the hospital, all assessments should be conducted per [Table 8-1](#). In addition, contact information for the patient and/or legal representatives should be obtained for the follow-up visits.

[figure not shown]
Screening assessments are to be taken as indicated in [Table 8-1](#) prior to randomization and are considered baseline measurements. Patients who meet the inclusion/exclusion criteria may be dosed immediately after obtaining the baseline measurements.

